Naturalistic Comparison of Group TBT and Group DSTs

An IRB-approved pilot trial was completed on group psychotherapy version of TBT compared to group DSTs in Canadian civilians with depressive/anxiety disorders ([name] et al., 2019). The study investigated 100 participants with various diagnoses of depressive/anxiety disorders that attended either Group TBT ($n = 34$) or Group DSTs for SOC, PD/AG, or OCD ($n = 66$). Participants in both treatments demonstrated significant improvements across all measures. Although no statistical differences were observed between groups, participants that received Group TBT demonstrated roughly twice the treatment effect size compared to participants in the DST groups, as presented in Table 4.

Table 4: Comparison of Group TBT and Group DSTs Across Depressive/Anxiety Disorders

Scale	TBT ($n = 34$) Within Group Outcome				Disorder-Specific ($n = 66$) Within Group Outcome				Between Groups	
	Pre M(SD)	Post M(SD)	t	d	Pre M (SD)	Post M (SD)	t	d	F	η_p^2
IIRS	63.5 (14.4)	48.5 (19.5)	4.0***	0.88	56.7 (17.7)	48.1 (19.4)	4.9**	0.46	1.2	.013

Note. *** $p < .001$; ** $p < .01$; * $p < .05$.

CSR&D CDA involving RCT of Individual TBT Compared to Behavioral Activation

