In addition to the unfunded pilot trials, [name] CSR&D CDA funded a small RCT to compare TBT with one specific individual DST, behavioral activation (BA), in Veterans with depressive/anxiety disorders. The study originally targeted a sample of 36 per group; however, the management of the grant and referral process allowed for a larger than expected sample to better test the hypotheses within the original timelines (TBT $n = 44$; BA $n = 46$). In contrast to the proposed study, this small RCT was designed to provide initial findings for TBT via an RCT with a single comparison group to inform future investigations. Results demonstrated reductions in outcome variables from pre-treatment to post-treatment for those in TBT. Large effects were found across all outcome variables. To examine the effects of treatment on several outcome variables (Table 5), linear mixed regression models were conducted using an intent-to-treat approach and handling missing data via robust maximum likelihood. Results revealed significant treatment effects from pre-treatment through 6-month follow-up, that were qualified by marginal to significant group by session effects for depression, anxiety, and somatic anxiety such that participants receiving TBT showed greater treatment gains on these outcome variables than did participants receiving BA. Although not significant, all other outcome variables favored TBT as well.

Table 5: Comparison of TBT and Behavioral Activation in Veterans with Depressive/Anxiety Disorders

	DASS-Stress B (SE)	DASS-Depression B (SE)	DASS-Anxiety B (SE)	STICSA-Cognitive B (SE)	STICSA-Somatic B (SE)	PCL-PTSD B (SE)	IIRS-Impairment B (SE)
Intercept	10.73* (0.76)	9.65* (0.87)	7.73* (0.82)	24.82* (1.04)	20.49* (1.02)	38.29* (2.56)	50.01* (2.44)
Group	-0.71 (1.06)	0.49 (1.10)	-1.39 (1.06)	-1.82 (1.34)	-1.64 (1.28)	-3.27 (3.45)	1.72 (3.53)
Session	-3.19* (0.67)	-3.54* (0.71)	-2.69* (0.61)	-5.08* (1.10)	-3.18* (0.62)	-10.27* (2.32)	-11.76* (2.19)
GrpXsess	0.62 (0.88)	1.49* (0.90)	1.59* (0.73)	1.89 (1.35)	1.66* (0.90)	3.43 (2.70)	1.69 (2.82)

Note. Intercept is centered on baseline session. GrpXsess = Group by session (baseline, post-intervention, 6-month follow-up [0, 1, 2]) interaction. * $p < .05$, † $p < .10$.

D. RESEARCH DESIGN AND METHODS

Table 6: Project Timeline

Proposed Component	Year	Timeframe
Preparing for RCT	Y01	month 01 – 06
Hiring staff	Y01	month 01 – 03
Training on procedures/protocols	Y01	month 03 – 06

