For all study outcomes (ADIS-5, IIRS, PCL-5, PDSS, PHQ-9, and STICSA), Veterans will be randomly assigned (1:1) to the TBT and specific DST conditions. The power analysis was calculated to be powered at 80% with a Bonferroni-corrected 1-tailed $\alpha = .006$ (.025/4 primary outcomes) to detect non-inferiority for TBT in comparison to the aggregated DST effect. Meta-analyses for CBT for MDD, CPT for PTSD, and CBT for PD/AG reveal large treatment effects (CBT for MDD bias-adjusted $g = .53$; Cuijpers et al., 2013; CPT for PTSD in military personnel $g = 1.33$; CBT for PD $g = 0.35$; Hofmann & Smits, 2008). Thus, the average effect size for DSTs was expected to range from small-to-medium to large. A power analysis was conducted using procedures recommended by Chow, Shao, and Wang (2017), Flight and Julious (2014), and Julious (2004) as well as recommendations by the United States Food and Drug Administration and the European Medical Association (Food and Drug Administration, 2017). An important topic in non-inferiority designs is selection of the “appropriate” prespecified non-inferiority limit. Current best practice involves selecting a non-inferiority margin that is not greater than the smallest effect size expected for the DSTs in comparison to a control condition. As a tradeoff between sample size needs and feasibility of recruitment, we conducted power analysis setting the non-inferiority margin to 0.5, indicating that we would consider TBT non-inferior to the DSTs if TBT were to perform less than half a standard deviation worse than the DSTs. We set the expected group different to 0.3 given our pilot data demonstrating that TBT outperforms DSTs by this margin across primary outcome variables. Using procedures recommended by Chow, Shao, and Wang (2017) for non-inferiority designs, which utilize the pre-specified non-inferiority margin (here prespecified as $\Delta d = 0.5$) and the estimated effect in the active comparison treatment ($d = 0.3$), we determined that 144 participants (72 per cell) would be needed. However, this does not account for potential attrition or for potential design effect issues involving therapist effects or for potential missing data related to telehealth delivery of services. To account for possible attrition and missing data as well as the potential influence of design effects, we increased the sample size to 306 participants based on the data available to date. Based on pilot data, we expect to find large within-person effects ($d \geq .80$) for TBT, indicating 4/5ths of a SD reduction in each of the primary outcome measures. This sample size would leave us powered to detect small-to-medium within-person effect sizes.

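### The pilots do not show the 0.3 SD TBT advantage assumed for the primary outcomes, and the stated 72 per cell for 80% power does not follow from the plan's inputs

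*Combined protocol and SAP*

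**What the plan says.** Under Sample Size Determination for Proposed Analyses (section D), the plan fixes four inputs.

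- Power: "The power analysis was calculated to be powered at 80" percent.
- Error rate: "Bonferroni-corrected 1-tailed $\alpha = .006$ (.025/4 primary outcomes").
- Margin: "we conducted power analysis setting the non-inferiority margin to 0.5".
- Expected difference: "We set the expected group different to 0.3 given our pilot data demonstrating that TBT outperforms DSTs by this margin across primary outcome variables". The next sentence describes the same 0.3 differently, as "the estimated effect in the active comparison treatment ($d = 0.3").

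From these it derives 144 participants, 72 per cell. It then raises the total to 306 for attrition, missing data and therapist design effects, giving no rate for any of them.

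Efficacy Measures Analyses names the PCL-5, PDSS, PHQ-9 and STICSA as the primary outcomes, makes end of treatment the primary time point, adjusts for the baseline value, and sets the margin at 0.

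Section C describes two pilots with a comparator. In the naturalistic study, Canadian civilians "attended either Group TBT ($n = 34$) or Group DSTs for SOC, PD/AG, or OCD ($n = 66"). The other was "a small RCT to compare TBT with one specific individual DST, behavioral activation (BA), in Veterans with depressive/anxiety disorders", with 44 and 46 participants.

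**The concern.** A non-inferiority trial gains power from any true advantage assumed for the new treatment, so that assumption needs evidence on the same outcomes and against the same comparators. Here the plan presents 0.3 SD as demonstrated on all the primary outcomes. If the pilots do not show it, the power statement has no stated basis. The reader also cannot tell how much of the increase from 144 to 306 is really available for attrition and clustering.

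**Working it through.** **1. What the pilots measured**

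| | Group study (Table 4) | Veteran RCT (Table 5) | This trial |
|---|---|---|---|
| Population | Canadian civilians | Veterans, depressive/anxiety disorders | Veterans, principal MDD, PTSD or PD/AG |
| Comparator | Group DSTs for SOC, PD/AG or OCD | Behavioral activation | CPT, CBT for MDD, CBT for PD/AG |
| Scales tabulated | IIRS only | DASS, STICSA, PCL, IIRS | PCL-5, PDSS, PHQ-9, STICSA |

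PHQ-9 and PDSS appear in neither. The IIRS is not one of the four primary outcomes. The group study found no statistical difference. No table gives a between-group d of 0.3.

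**2. What Table 5 implies**

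The table note says "Intercept is centered on baseline session", with sessions coded 0, 1, 2. Write G for the Group coefficient and I for group by session. The text says TBT gained more, so I infer BA = 1 and TBT = 0; positive values then favour TBT. No SDs are printed, so I approximate SD = SE(G) / sqrt(1/44 + 1/46) = 4.74 × SE(G).

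- Difference in change to post-treatment = I, with z = I/SE(I).
- Raw post-treatment difference = G + I.
- Baseline-adjusted post-treatment difference = G + I − r × G, with assumed baseline-post correlation r from 0.3 to 0.7.

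| Scale | SD | I (SE) | p | I in SD | G + I | Adjusted, in SD |
|---|---|---|---|---|---|---|
| PCL | 16.4 | 3.43 (2.70) | 0.20 | 0.21 | −3.27 + 3.43 = 0.16 | 0.07 to 0.15 |
| STICSA-Cognitive | 6.4 | 1.89 (1.35) | 0.16 | 0.30 | −1.82 + 1.89 = 0.07 | 0.10 to 0.21 |
| STICSA-Somatic | 6.1 | 1.66 (0.90) | 0.065 | 0.27 | −1.64 + 1.66 = 0.02 | 0.08 to 0.19 |

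Example, PCL at r = 0.5: 0.16 + 0.5 × 3.27 = 1.80 points, and 1.80/16.4 = 0.11 SD. The somatic term carries a significance mark in the text available to me, but its printed estimate and SE do not reach two-sided .05. The note also defines a mark for p < .10, so the symbol may have been misread.

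**3. Reproducing 72 per cell**

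Normal approximation, SD 1, equal arms, D = true TBT advantage:

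n per arm = 2(z_α + z_β)² / (0.5 + D)², with z_α = 2.498 (one-sided .00625) and z_β = 0.842, so the numerator is 22.3.

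- D = 0.3: 22.3/0.64 = 35 per arm (36 at .006).
- D = 0: 22.3/0.25 = 90 per arm.
- D = −0.3 (TBT worse): 22.3/0.04 = 558 per arm (563 at .006).

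None gives 72. Among the variants tried, only one-sided .025 with 85% power and zero difference does, and those are not the stated inputs.

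**4. Power at margin 0.5**

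Power = Φ[(0.5 + D) × sqrt(n/2) − 2.498].

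| Effective n per arm | D = 0 | D = 0.3 |
|---|---|---|
| 72 (stated) | Φ(3.00 − 2.498) = 69% | Φ(4.80 − 2.498) = 98.9% |
| 107 (30% loss from 153) | 88% | above 99% |
| 153 (306 in total) | 97% | above 99% |
| 107/1.5 = 71.3 (30% loss, design effect 1.5) | Φ(2.986 − 2.498) = 69% | not needed |

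The 30% loss and the design effect of 1.5 are illustrations; the plan gives neither. With no loss but a design effect of 2, the plan's own warning level, 153/2 = 76.5 gives Φ(3.092 − 2.498) = 72%.

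**5. Power at margin 0**

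Power = Φ[D × sqrt(n/2) − 2.498]. At D = 0 it is 0.6% for any n. At D = 0.3 with 153 per arm it is Φ(2.624 − 2.498) = 55%.

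**The case against.** The best defence is that 0.3 has a visible source. Differences in change in Table 5 are about 0.21 to 0.30 SD on the PCL and STICSA, and the 6-month differences are similar (0.22 to 0.31). DASS-Depression, though not the PHQ-9, gives about 0.29. The sponsor also notes that the RCT used a single control DST and was meant to give initial findings. All this stands, and it makes 0.3 a reasonable optimistic scenario. It does not make it demonstrated: the 95% intervals for the three interactions, about −0.11 to 0.53, −0.12 to 0.71 and −0.02 to 0.56 SD, all include zero.

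A reader might infer stronger things that the documents do not support:

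- **That the pilots show no post-treatment difference.** The raw contrasts of 0.16, 0.07 and 0.02 points are near zero because TBT started worse on these scales. They are also predictions from a single linear slope, not observed means. The planned analysis adjusts for baseline, and on that basis the values are below 0.3 but not zero.
- **That the pilots were in other disorders.** The Veteran RCT enrolled depressive/anxiety disorders, a category that section B says includes PTSD, MDD and PD/AG, and the group study included PD/AG. The firm gaps are the comparators and the missing scales.
- **That the stated 80% depends on 0.3.** At 72 per cell, 80% needs only (2.498 + 0.842)/6 − 0.5 = 0.057 SD. Even the lowest adjusted value, 0.07, gives Φ(0.57 × 6 − 2.498) = 82%. That comfort covers only the PCL and STICSA, and only against behavioral activation.

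Zero true difference is a planning convention, not a requirement.

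**Conclusion.** The claim of a demonstrated 0.3 SD advantage on the primary outcomes is unsupported: two of the four have no comparative pilot data, and the other two show about 0.07 to 0.21 SD on the planned baseline-adjusted contrast. Those values rest on inferred SDs and group coding and an assumed correlation. Table 5 also does not say which PCL version was used, so its relevance to the PCL-5 is itself assumed.

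Separately, 72 per cell for 80% power does not follow from the stated inputs under any reading of 0.3.

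This does not show that the trial is too small. At margin 0.5 and zero difference, 306 gives 97% before loss and clustering. It could fall to about 69% if a 30% loss and a design effect of 1.5 both applied, and the plan gives no rates from which to tell. The point is worth acting on because it corrects a figure that the trial relies on.

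**What to change.** 1. Reconcile the margin first: 0.5 in the sample size section against 0 in Efficacy Measures Analyses. A zero-difference base case has no meaning at margin 0.
2. Remove the statement that pilot data demonstrate the advantage on the primary outcomes. Say that the pilots reported no PHQ-9 or PDSS, did not use CPT or CBT for MDD, and did not establish a difference on the PCL or STICSA.
3. Take zero true difference as the base case, keep 0.3 as a labelled optimistic scenario, and describe 0.3 in one way only.
4. Replace the 144 and 80% statement with recomputed power at margin 0.5: 97% for 153 per arm with no loss or clustering, then power after a stated attrition rate and a stated therapist design effect. Worked examples are 88% at 107 per arm, and 69% at 107 per arm with a design effect of 1.5.
5. Use one arm size throughout. Randomization Procedures gives 108 per arm, while 306 at 1:1 is 153.

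The cost is rewording and a short recalculation. The correction itself adds no patients; the downside is a less favourable stated power.

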Participants who meet inclusion/exclusion criteria will be randomized into a study condition and will be assigned to a project therapist. Because most VAMC patients who meet study criteria likely will present with multiple depressive/anxiety disorders (Brown et al., 2001), principal diagnosis, or the most impairing of the diagnosable disorders, will be used to inform randomization. Principal diagnosis will be determined via diagnostic severity scores in the Anxiety Disorders Interview Schedule-5 (ADIS-5) (Brown, 2014). To balance diagnoses across the two conditions, a stratified random assignment based on principal diagnosis will be used (MDD, PTSD, and PD/AG) ([name], 2015). Based on referrals to the PI's CDA, it is expected that at least 45% of the recruited Veterans will have served in OEF/OIF and $\geq 50\%$ will be representative of minority groups.

Eligible VAMC patients will be randomized into one of two treatment conditions: TBT or DSTs. Both treatment conditions will include 12 weekly 45- to 60-minute treatment sessions. Both treatment conditions will be delivered either in-person and via VA-approved telehealth technologies, based upon the preference of the participant. The general format of sessions will involve: 1) brief check-in; 2) review of materials from previous sessions; 3) review of homework assignments; 4) overview of new materials and in-session exercises; and 5) assignment of homework for next session. Attendance and homework completion will be recorded.

Randomization Procedures

Participants will be randomly assigned (1:1) to one of the two study arms ($n = 108$ per arm) using a permuted block randomization procedure. Randomization will be stratified by diagnostic group (PTSD, PD/AG, MDD) and block size will be varied to minimize the likelihood of unmasking. After determining eligibility and completing consent and baseline assessment materials, enrolled participants will be assigned to their treatment condition by the Research Project Therapist/Coordinator using a computer-generated randomization scheme. Once a participant is randomized, they will be included in the modified intent-to-treat (MITT) analysis. The Research Project Therapy/Coordinator and the statistical analyst in charge of randomization ([name]) will be the only

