The continuous measures included measures of disorder severity scales (ADIS-5), disorder-specific symptomatology (PCL-5, PDSS, PHQ-9, and STICSA), general related symptomatology (STISCA), and quality of life and impairment (IIRS). Of these variables, the PCL-5, PDSS, PHQ-9, and STICSA are the primary outcomes of interest. All other analyses will be conducted in an exploratory fashion to inform future studies and compare findings to previous studies ([name], 2014; [name] et al., 2017; 2019). Parameter estimates to calculate the effect size difference will be arrived at using three-level (measurement occasions nested within participants nested within assigned treatment condition) generalized mixed-effects regression models (MRM). MRM is a method of repeated measures analyses that allows for modeling of continuous and categorical independent and dependent variables and for appropriate modeling of covariance structures when observations are correlated across time and/or across condition. This analytic approach fully captures variability in outcomes across multiple follow-up assessments and accounts for any potential effect of the group to which a participant is assigned and is thus preferred over methods that collapse data over time. We will calculate between-group treatment differences as Cohen's d, based on the effect of treatment condition on the intercept parameter when the model is centered on post-intervention and on the effect of treatment condition on the intercept parameter when the model is centered on month 6. We prespecified the non-inferiority margin (d) to be 0 (indicating we expected TBT to be at least equivalent to the aggregate DST effect) and the one-sided CI for our four primary analyses at $\alpha = .006$. In the primary analyses of outcome variables, we will covary for the baseline value of the variable of interest. We also will include the linear effect of time as well as a time by condition interaction effect to determine whether treatment differences (or lack thereof) were stable from post-intervention through the follow-up. Additional covariates (e.g. age, number of psychiatric comorbidities, race, sex, combat theatre, number of treatment sessions, specific DST received) will be added to the model to adjust for putative confounding variables. Effect size CIs that do not contain 0 provide evidence in support of noninferiority for TBT. The primary outcome time point is at the end of the active treatment phase and the secondary time point is at the end of the naturalistic 6-month follow-up period. Further, within-subject effect sizes from baseline to post-intervention and to 6-month follow-up also will be calculated within the TBT condition to quantify TBT-specific reductions in symptoms. These analyses will be probed to examine potential therapist effects. First, design effects will be calculated for the primary outcome variables. Design effects > 2 are often used as a heuristic to judge when these effects can be problematic.

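### The stated sample-size inputs give about 72 participants in total (36 per arm), not 144 (72 per cell), and the randomization section's 108 per arm contradicts the planned 306

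*Combined protocol and SAP*

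**What the plan says.** Sample Size Determination for Proposed Analyses gives every input for a two-arm non-inferiority comparison of means: 80% power, a one-tailed Bonferroni-corrected alpha of .006 (.025/4), and 1:1 allocation. On the margin: "we conducted power analysis setting the non-inferiority margin to 0.5". On the expected difference: "We set the expected group different to 0.3 given our pilot data demonstrating that TBT outperforms DSTs by this margin across primary outcome variables". Shortly afterwards the same 0.3 is called "the estimated effect in the active comparison treatment". The result is "we determined that 144 participants (72 per cell) would be needed".

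The section then says that "this does not account for potential attrition or for potential design effect issues involving therapist effects", and adds missing data related to telehealth to the list of things left out. To cover these, "we increased the sample size to 306 participants based on the data available to date". No retention rate, intraclass correlation, design effect or multiplier is given.

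The total of 306 also appears in the study overview ahead of section B, in Intake Procedures, in Risks to the Subjects and in the Targeted/Planned Enrollment Table. Randomization Procedures differs: "Participants will be randomly assigned (1:1) to one of the two study arms ($n = 108$ per arm".

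**The concern.** Two figures in the current text do not fit the rest of the plan. First, the pre-inflation sample size is about twice what its own inputs produce, so a reader cannot reproduce it or tell which input or output is at fault. The double description of the 0.3 adds to this, because a between-arm difference and an effect of the comparator play different parts in a non-inferiority calculation. Second, the section that governs allocation gives an arm size 45 below the one implied by the enrolment target.

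At stake is whether the justification for 306 can be checked, and whether the randomization scheme is prepared for 216 or 306 participants. The plan also expects possible therapist clustering and attrition without putting numbers on them, so the room that each total leaves for these cannot be read from the text.

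**Working it through.** **Inputs (Sample Size Determination).** Power 0.80, z = 0.8416. One-sided alpha .006, z = 2.5121 (.025/4 is exactly .00625). Margin 0.5 SD. Expected difference 0.3 SD in favour of TBT. Allocation 1:1. SD = 1, since margin and difference are in SD units.

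**Formula.** n per arm = 2 × (z for alpha + z for power)² / (margin + TBT advantage)².

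**Attempt to reproduce the plan's figure.** The distance from the margin is 0.5 + 0.3 = 0.8.

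- alpha .006: 2 × (2.5121 + 0.8416)² / 0.8² = 22.495 / 0.64 = 35.15, so 36 per arm, 72 in total
- alpha .00625: 34.85, so 35 per arm, 70 in total
- noncentral t, either alpha: 37 per arm, 74 in total

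The stated 72 per cell (144) is not reproduced; it is about twice the result.

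**Power that 72 per arm would have.** 0.8 × √(72/2) − 2.5121 = 4.8 − 2.5121 = 2.288, which is 98.9% (98.7% by noncentral t).

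**Other readings of the 0.3, at the same alpha (.006), power and margin.**

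| Assumed true difference | Distance | n per arm |
|---|---|---|
| TBT better by 0.3 | 0.8 | 36 |
| No difference | 0.5 | 22.495/0.25 = 89.98, so 90 |
| TBT worse by 0.3 | 0.2 | 22.495/0.04 = 562.4, so 563 |

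None gives 72. Solving backwards, 72 per arm needs a distance of √(22.495/72) = 0.559, that is, TBT better by 0.059 SD, which the plan does not state.

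**Arm size.** 2 × 108 = 216. 306 / 2 = 153. The gap is 306 − 216 = 90 in total, 45 per arm.

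**Clustering each total can absorb.** With TBT better by 0.3 and margin 0.5, 80% power holds while (arm size × retention) / design effect is at least 35.15. Retention of 70–80% is an assumption. The nearest figures in the documents are the pilot treatment-completion rates of 72.4% and 80.0% in Initial Pilot of TBT Protocol, and these are not assessment retention.

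| Total | Retention | Retained per arm | Largest design effect keeping 80% power |
|---|---|---|---|
| 216 | 70% | 75.6 | 75.6/35.15 = 2.15 |
| 216 | 80% | 86.4 | 86.4/35.15 = 2.46 |
| 306 | 70% | 107.1 | 107.1/35.15 = 3.05 |
| 306 | 80% | 122.4 | 122.4/35.15 = 3.48 |

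Efficacy Measures Analyses (Primary Aim) names design effects above 2 as the region of concern, so the gap between 216 and 306 falls where the plan itself expects possible trouble.

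**The case against.** The strongest reply is that little follows from the 144. On the plan's own inputs it errs on the safe side, it is an intermediate number, and the enrolment target is 306 in five places. That stands: the 144 alone is a problem of reproducibility, and because no multiplier to 306 is given, correcting it has no demonstrated effect on 306.

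A second reply is that an unstated input may explain the figure. Some combinations do give 72 per arm, for example alpha .025 with 85% power and no difference, or margin 0.3 with alpha .003. Baseline adjustment is also planned ("we will covary for the baseline value of the variable of interest"). Under no difference, a baseline correlation of √(1 − 72/89.98) = 0.45 would bring 90 down to 72. Each of these replaces a stated input, and at the stated 0.3 advantage baseline adjustment would lower 36 and widen the gap. They do not rescue the text, but they show that the output need not be the wrong part.

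Three stronger readings are tempting and are not supported.

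- A reader might infer that the formula's total of 72 was mistaken for a per-cell number. The match is suggestive, but the documents do not say so.
- A reader might infer that 108 per arm is left over from inflating 144 for one-third loss (144 / (2/3) = 216). This too is only inference.
- A reader might infer that the trial is underpowered, especially if TBT has no true advantage. The plan assumes an advantage of 0.3, fixes neither retention nor design effect, adjusts for baseline, and uses full information maximum likelihood on all randomized participants, so partly observed participants still contribute. The documents do not show that 306 falls short.

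**Conclusion.** Both discrepancies hold. The stated inputs give about 72 participants in total (70 to 74), against 144 stated, a factor of about 2. The arm size in Randomization Procedures is 45 below what 306 implies, a gap of 90 overall. The first result rests on reading the 0.3 as an advantage for TBT, which the section says outright; no other reading at the stated alpha, power and margin gives 72 per arm.

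The error in the 144 is conservative. Given the 0.3 advantage, the 0.5 margin and assumed retention of 70–80%, without baseline adjustment, 306 keeps 80% power up to a design effect of about 3.05 to 3.48. For 216 the limit is about 2.15 to 2.46, so it would be too much to say that either total is safe whatever the clustering. All these figures presuppose the 0.5 margin. Efficacy Measures Analyses (Primary Aim) sets the margin at 0, and that conflict is a separate point.

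**What to change.** 1. Define the 0.3 once, as the assumed TBT-minus-DST difference, with its direction, and remove the description of it as an effect of the comparator.
2. State the formula, the exact alpha (.006 or .00625) and every input, and correct whichever is wrong so that inputs and base number agree. If the stated inputs stand, the base is about 72 in total (36 per arm).
3. Restate the power of the planned 306 with the retention rate and design effect used, and the reason for each.
4. Change the arm size in Randomization Procedures to 153, to agree with 306, and check that the randomization scheme was generated for that number.

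The cost is a wording amendment to the combined protocol and SAP. Planned enrolment does not change.

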
Analysis Plan – Treatment Outcome Symptomatology and Feasibility

Preliminary Descriptive Analyses

Univariate descriptive statistics and frequency distributions will be calculated as appropriate for all relevant variables to identify potential departures from distributional assumptions of proposed analyses. If necessary, appropriate data transformations will be applied, or alternative analysis procedures (e.g., nonparametric) will be used. Baseline values for demographic, symptom variables, and related impairments will be described via frequency distributions for categorical variables, measures of central tendency (mean, median), and variability for the total sample and within race groups. The baseline variables will be compared between intervention groups using t-tests (or Wilcoxon rank sum tests) for continuous outcomes and chi-square (or Fisher's Exact Test) for categorical variables.

Missing Data

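### The plan lets the primary outcomes be transformed or ranked after their distributions are seen, although non-inferiority is judged on Cohen's d against a margin in SD units

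*Combined protocol and SAP*

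**What the plan says.** Three parts of section D bear on this point.

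- **Preliminary Descriptive Analyses.** Distributions are examined "for all relevant variables to identify potential departures from distributional assumptions of proposed analyses". If that shows a need, "appropriate data transformations will be applied, or alternative analysis procedures (e.g., nonparametric) will be used". The section gives no trigger, names no transformation, does not require the decision to be taken blind to arm, and does not say how a margin would carry over.
- **Sample Size Determination for Proposed Analyses.** The margin is put in SD units: "we would consider TBT non-inferior to the DSTs if TBT were to perform less than half a standard deviation worse than the DSTs". It names no SD and gives no scale points.
- **Efficacy Measures Analyses (Primary Aim).** The effect measure is set out as follows: "We will calculate between-group treatment differences as Cohen's d, based on the effect of treatment condition on the intercept parameter". The model is a mixed-effects regression with the baseline score as covariate. The SD that divides the effect is not named. The margin here differs: "We prespecified the non-inferiority margin (d) to be 0". The decision rule follows it: "Effect size CIs that do not contain 0 provide evidence in support of noninferiority for TBT".

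Missing Data handles incomplete outcomes by full-information maximum likelihood. None of these sections exempts the four primary outcomes from the option to transform or use ranks.

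**The concern.** A non-inferiority verdict compares a confidence limit with a margin, and both must be on one scale that is fixed in advance. Here the scale can change after the outcome distributions have been examined. Half an SD of raw scores, half an SD of log scores and a shift in ranks are three different amounts of lost benefit. An ordinary rank test would also drop the baseline covariate and the maximum-likelihood treatment of missing data on which the planned model relies.

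Skew is a realistic prospect. Eligibility needs only one of the three disorders, all randomized participants are analysed, and the PDSS and PCL-5 are primary outcomes for the whole sample, so some participants may score near the floor. At stake is whether a verdict of non-inferiority could be defended against the charge that the scale was picked after the data were seen.

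The missing denominator for d is a second open choice, but it matters only if the margin is not zero.

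**Working it through.** The plan states no margin in points and no SD for d, so there is no figure of its own to reproduce. Its sample size of 72 per cell does not enter this check.

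**1. What a log scale does to the margin.** Input: PTSD Checklist after treatment in Table 3, mean 33.7, SD 10.9. Treating scores as log-normal (assumed), SD(log) = √ln(1 + (10.9/33.7)²) = 0.315. Half of that is a ratio of exp(0.5 × 0.315) = 1.17. The tolerated deficit is then about 3.4 points at a score of 20 and about 10.2 points at a score of 60. On raw scores it is the same number of points everywhere.

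**2. Direction.** Assumed floor-heavy scale limited to 0–28: one third on-target (mean 10, SD 5), the rest exponential with mean 3; 400,000 per arm; log(x + 1); pooled SD.

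| TBT deficit | d raw | d log | d ranks |
|---|---|---|---|
| 9 points, on-target third only | 0.43 | 0.25 | 0.24 |
| 2 points, everyone | 0.40 | 0.60 | 0.53 |

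The first pattern moves a result towards non-inferiority after transformation; the second moves it away.

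**3. The unnamed SD, if the margin is 0.5.** Table 3 gives PTSD Checklist SDs of 14.8 before and 10.9 after treatment. Half an SD is 0.5 × 14.8 = 7.4 points or 0.5 × 10.9 = 5.45 points. Take 306/2 = 153 per arm, an assumed baseline–post correlation of 0.5, and one-sided α = .025/4 = .00625 (z = 2.498):

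- residual SD = 10.9 × √0.75 = 9.44;
- half-width = 2.498 × 9.44 × √(2/153) = 2.70;
- an observed TBT deficit of 3 points has an upper limit of 5.70 points;
- 5.70/14.8 = 0.38 (passes), 5.70/10.9 = 0.52 (fails), 5.70/9.44 = 0.60 (fails).

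With the 108 per arm given under Randomization Procedures, a 2.5-point deficit splits the same way: upper limit 5.71 points, or 0.39, 0.52 and 0.60.

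**4. How often verdicts differ.** 2,000 simulated trials per scenario, 153 per arm, baseline-adjusted model, gamma-shaped post scores (mean 25 assumed, SD 10.9), baseline SD 14.8, correlation 0.5. Pass rates at margin 0.5 with a true TBT deficit of 3 points:

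| Analysis | Pass rate |
|---|---|
| Raw, baseline SD | 94% |
| Raw, post SD | 39% |
| Raw, residual SD | 19% |
| Square root | 32% |
| Log | 27% |
| Mann-Whitney, margin mapped to Φ(0.5/√2) | 19% |

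- The methods disagreed in 81% of datasets: in 75% from the choice of SD alone, and in 27% from transformation or ranks alone (against raw scores with the post SD).
- With no true difference, they disagreed in 6%.
- With TBT better by about 0.3 SD, the planning assumption, they disagreed in about 0%.

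**5. The same data at margin 0.** Dividing by any positive SD leaves the sign of d and of its limit unchanged, so the choice of SD never alters the verdict. Raw, log, square-root and rank analyses still disagreed in 29% of datasets with TBT better by about 0.3 SD, and in about 1% with no difference.

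**The case against.** The strongest reply is that the section with the decision rule sets the margin at 0, and under that rule the SD question has no effect on the verdict. That stands. It would be tempting to say that the margin simply is half an SD, but the documents give two values. The SD part of this point is conditional on how they are reconciled.

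A reader might also infer that transforming favours TBT. The documents do not support that. It needs a large deficit confined to the on-target participants. A uniform shift reverses it, and in the simulation at margin 0.5 the log analysis passed less often than raw scores with the post SD (27% against 39%).

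Nor is the option certain to be used. It applies only if necessary, mixed models assume normal residuals rather than normal scores, the efficacy section names a default (generalized) mixed model, and the protocol expects most participants to have several disorders, which weakens the floor argument. All of this lowers the chance that the option is used. None of it limits what may be done if it is.

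The pilot SDs are also a thin basis. They come from the 17-item checklist in a small sample, not from the PCL-5. In Table 3 the IIRS SDs move the other way (13.7 before, 17.0 after), and in Table 2 the checklist SDs are close (13.1 and 14.0). They show that the choice of SD can matter, not by how much it will.

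**Conclusion.** The point holds in this form. The plan permits a change of scale or method for the primary outcomes after their distributions are inspected, while the effect measure and margin are in SD units that do not carry over to a log or rank scale. The verdict can therefore depend on a choice made after seeing outcome data, in a direction that cannot be stated in advance.

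The size depends on the margin and on the truth. At 0.5, the exposure is large when TBT is moderately worse (81% disagreement at a 3-point deficit in the example), small when the arms are equal (6%), and practically nil at the planned advantage of 0.3. At 0, only the transformation or rank option matters, with 29% disagreement at that advantage. These percentages rest on the assumed correlation, distribution shape and mean, and on the pilot SDs. The missing SD taken alone would be mainly an omitted detail. It becomes decisive only with a non-zero margin.

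**What to change.** 1. **Preliminary Descriptive Analyses.** State that the four primary outcomes are analysed on their original scores with the mixed model of the efficacy section, whatever their distribution, using robust or bootstrap confidence limits. Transformed and rank analyses become sensitivity analyses that do not decide non-inferiority.
2. **Sample Size Determination and Efficacy Measures Analyses.** Reconcile the margins of 0.5 and 0, and make the decision rule match.
3. **Efficacy Measures Analyses, if a non-zero margin is kept.** Name one SD as the denominator of d and give each margin in scale points as well. The pooled baseline SD of all randomized participants is one reasonable choice; any SD fixed in advance closes the gap.

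The cost is SAP wording, plus limits that may be slightly wider than model-based ones. The change should be dated before anyone sees outcomes by arm, because afterwards it would no longer be credible.
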